6.4 Early Withdrawal Procedures

If a subject is withdrawn from the study before study completion, all procedures scheduled for the final visit (Day 28 ± 5 days) should be performed if possible.

6.5 Training

Extensive training will be provided to all study staff. Initial training will occur at the Site Initiation Visit, followed by on-site training that will take place during the initial surgical procedures with Sponsor Representatives present in the operating room during the procedures. Sponsor Representatives will ensure all study personnel are adequately trained and follow identical procedures to preserve the integrity of the collected data without providing input on the selection of specimens or their fluorescent status, these tasks are the sole responsibility of the operating surgeon. Additional retraining may take place if necessary throughout the course of the study. Training will include a review of protocol procedures, NIR camera operating instructions, documentation of specimens and their fluorescence status, and upload of source documentation. All training will be documented and stored within the Trial Master File.

7. STUDY ASSESSMENTS

7.1 Demographic Data/Medical History

Demographic data and a complete medical history (including drug, alcohol, and tobacco use, as well as current use of herbal supplements and multivitamins) will be obtained at Screening.

7.2 Physical Examination

A complete physical examination will be performed at Screening and on Day 10 (± 5 days) or Day of Discharge. The complete physical examination may include the following organ or body system assessments: skin; head; eyes; ears; nose; throat; thyroid; neurological; chest and lungs; cardiovascular; abdomen (liver and spleen); lymph nodes; musculoskeletal; and extremities.

7.3 Weight and Height

Body weight (kg) and height (m) will be measured at Screening and at Day 0 prior to dosing. The subject's body mass index (BMI) will be calculated in the eCRF at Screening using the following formula:

$$BMI = \frac{Weight \ (kg)}{(Height \ [m])^2}$$

7.4 Vital Sign Measurements

Vital sign measurements (systolic and diastolic blood pressure, pulse, respiratory rate, and oral temperature) will be obtained at Screening, Day 0 (Pre/Post dose), Day of Surgery (only if abnormal at dosing), Day 10 (± 5 days) or Day of Discharge and Day 28.

Oral temperature will be documented in degrees Celsius.

Blood pressure and pulse will be measured after a resting period of at least 5 minutes in the supine position with a standard mercury sphygmomanometer or an automated oscillometric blood pressure monitor.

7.5 12-lead Electrocardiogram

A standard safety 12-lead ECG will be conducted on Day 0 (Pre-Dose) and on Day 10 (± 5 days) or Day of Discharge. Additional ECGs may be performed at the discretion of the investigator. The investigator or designee will be responsible for reviewing the ECG to assess whether the ECG is within the reference limits and to determine the clinical significance of the results. These assessments will be recorded in the eCRF.

7.6 Clinical Laboratory Tests

Clinical laboratory tests (hematology and serum chemistry) will be performed by a Local and/or Central Laboratory. Blood samples will be collected at Screening, on Day 0, Day of Surgery, Day 10 (± 5 days) or Day of Discharge and on Day 28.

7.6.1 Pregnancy Tests

For female subjects, a serum sample will be collected for a serum pregnancy test (β -human chorionic gonadotropin) at Screening and blood samples will be collected for pregnancy tests on Day 0, and on Day 28. Negative pregnancy test results will be required for subjects to enroll and continue study participation.

7.6.2 Laboratory Measurements

The following clinical laboratory parameters will be measured:

Clinical Chemistry	Hematology
Total protein	Hemoglobin
Albumin	Hematocrit
Blood urea nitrogen (BUN)	Erythrocyte count (red blood cells)
Calcium (total and ionized)	Differential leukocytes
Creatinine	Platelet count
Creatine kinase	Total leukocytes (white blood cells)
Chloride	
Total bilirubin	
Alkaline phosphatase	
Glucose	
Sodium	
Potassium	
Inorganic phosphate	
Lactate dehydrogenase	
Total Cholesterol	
Gamma-glutamyl transferase	
Alanine aminotransferase (ALT)	
Aspartate aminotransferase (AST)	

8. REPORTING ADVERSE EVENTS

All adverse events (AEs) will be recorded in the eCRF, whether they are observed by the investigator, reported by the subject, observed from laboratory findings, or collected by other means. Adverse events will be monitored beginning on Day 0 through the end of the study (Day 28). Adverse events will be graded by the Investigator using a numerical score according to the defined National Cancer Institute Common Terminology Criteria for Adverse Events (NCI CTCAE) Version 5.0 (2017).

8.1 Definitions

The investigator is responsible for reporting all AEs that are observed or reported during the study, regardless of their relationship to study drug or their clinical significance.

An AE is defined as any untoward medical occurrence in a subject enrolled into this study regardless of its causal relationship to study treatment. Subjects will be instructed to contact the principal investigator if any symptoms develop.

A treatment-emergent AE (TEAE) is defined as any event not present before the first exposure to the study drug or any event already present that worsens in either intensity or frequency following the first exposure to the study drug.

All AEs that occur beginning on Day 0 must be reported in detail in the eCRF and followed to satisfactory resolution or until the principal investigator deems the event to be chronic or the subject to be stable. The description of the AE will include the onset date, duration, date of resolution, severity, seriousness, etiology, and the likelihood of relationship of the AE to study drug.

A serious adverse event (SAE) is defined as any event that results in any of the following outcomes:

- Results in death
- Is life threatening, i.e., the subject was, in the opinion of the investigator, at risk of death at the time of the event; it does not refer to an event that, hypothetically, might have caused death if it had occurred in a more severe form
- Requires inpatient hospitalization or prolongs existing hospitalization
- Results in persistent or significant disability and/or incapacity
- Is a congenital anomaly/birth defect
- Is an important medical event

Important medical events that may not result in death, be life threatening, or require hospitalization may be considered an SAE when, based upon appropriate medical judgment, they may jeopardize the subject and may require medical or surgical intervention to prevent one of the outcomes listed in this definition. Examples of such medical events include allergic bronchospasm requiring intensive treatment in an emergency room or at home, blood dyscrasias, convulsions that do not result in inpatient hospitalization, or the development of drug dependency or drug abuse.

8.2 Adverse Event Reporting

All AEs reported or observed during the study will be recorded in the eCRF. Information to be collected includes drug treatment, dosage, type of event, time of onset, investigator-specified assessment of severity and relationship to study drug, time of resolution of the event, seriousness, any required treatment or evaluations, and outcome. Adverse events resulting from concurrent illnesses, reactions to concurrent illnesses, reactions to concurrent medications, or progression of disease states must also be reported. All AEs will be followed to adequate resolution.

Any medical condition that is present at the time that the subject is screened but does not deteriorate should not be reported as an AE. However, if the condition deteriorates at any time during the study after the first exposure to study drug, it should be recorded as an AE.

8.3 Assessment of Causality

The investigator's assessment of an AE's relationship to study drug is part of the documentation process, but it is not a factor in determining what is or is not reported in the study. If there is any doubt as to whether a clinical observation is an AE, the event should be reported.

The relationship or association of the study drug in causing or contributing to the AE will be characterized using the following classification and criteria:

- Unrelated: This relationship suggests that there is no association between the study drug and the reported event
- Unlikely: This relationship suggests the temporal association between the AE and the study drug is such that the study drug is not likely to have any reasonable association with the AE
- Possible: This relationship suggests that treatment with the study drug caused or contributed to the AE, i.e., the event follows a reasonable temporal sequence from the time of study drug administration and/or follows a known response pattern to the study drug, but could also have been produced by other factors
- Probable: This relationship suggests that a reasonable temporal sequence of the event with study drug administration exists and, based on the known pharmacological action of the drug, known or previously reported adverse reactions to the drug or class of drugs, or judgment based on the investigator's clinical experience, the association of the event with the study drug seems likely
- Definite: This relationship suggests that a definite causal relationship exists between the study drug administration and the AE, and other conditions (concurrent illness, progression/expression of disease state, or concurrent medication reaction) do not appear to explain the event

8.4 Assessment of Severity

The intensity of the AE will be rated as mild, moderate, or severe using the following criteria:

- Mild: These events require minimal or no treatment and do not interfere with the subject's daily activities
- Moderate: These events result in a low level of inconvenience or concern with the therapeutic measures. Moderate events may cause some interference with functioning
- Severe: These events interrupt a subject's usual daily activity and may require systemic drug therapy or other treatment. Severe events are usually incapacitating

Changes in the severity of an AE should be documented to allow an assessment of the duration of the event at each level of intensity to be performed. Adverse events characterized as intermittent require documentation of onset and duration of each episode.

8.5 Serious Adverse Event Reporting

All SAEs must be reported to the email within 24 hours from the time site personnel first learn about the event. Additional follow-up information, when available, should also be sent to .

8.5.1 SAE Reporting Contact Information

Serious Adverse Event Report Forms must be submitted within 24 hours and should consist of the trial provided Serious Adverse Event Report Form. The following information should be entered into the EDC database at the time the SAE form is submitted: the demographics page(s), the medical history page(s), the AE page(s) and the concomitant medications page(s). If the subject is hospitalized because of or during the course of an SAE then a copy of the hospital discharge summary should be provided to the email as soon as it becomes available. Withdrawal from the study and all therapeutic measures will be at the discretion of the principal investigator. All SAEs, regardless of relationship to the study drug, will be followed until satisfactory resolution or until the investigator deems the event to be chronic or the subject to be stable.

9. STATISTICAL METHODS

Additional statistical analyses, other than those described in this section, may be performed if deemed appropriate. Details of the analyses are described in the statistical analysis plan.

9.1 Sample Size

The sample size for this study was originally 40 subjects. This sample size is based on historical experience with similar pilot studies with the goal of informing power calculations for future studies. This study is not formally powered for hypothesis testing. While the original sample size of 40 subjects would be sufficient for developing further understanding of the endpoints described herein, increasing the amount of subjects to approximately 60 will provide superior estimates for endpoints to power future studies. Sample size calculations account for non-evaluable and drop-out patients.

9.2 Populations

All subjects who receive any dose of the study drug will be included in the intent to treat population. The efficacy population will consist of all subjects who receive >75% of the intended dose of pegasitacianine, had a minimum of one (1) image collected during their procedure, and had the opportunity for post-SOC exploration of the peritoneal cavity. The safety population will include all subjects who were administered pegasitacianine whether it be a full or partial dose.

9.3 Rate of Clinically Significant Events

Determining the rate of clinically significant events (CSE) detected by pegasitacianine at the subject-level is the primary objective of this study. CSEs will include pegasitacianine detection of

occult disease not otherwise known by the surgeon to exist, the detection of a positive surgical margin, and accurate identification of tumor negative SOC biopsies. A list of CSEs and their definitions is provided below.

- Detection of Occult Disease or Positive Surgical Margins – identification of tumor-containing tissue due to pgsitacianine fluorescence, confirmed via histopathological analysis, that otherwise went undetected during pre-operative imaging (PET, MRI) or by the surgeon during SOC surgery
 - This occurs when a sample that (1) exhibits fluorescence *in situ* and (2) is pathologically-confirmed as a tumor, is obtained by fluorescence during SOC surgery.
- Tumor Negative SOC Biopsies – during SOC surgery, the surgeon will collect tissue specimens that are suspicious for disease. If those samples do not demonstrate pgsitacianine fluorescence and are found to be devoid of tumor pathologically, those specimens would be included as a tumor negative SOC biopsy
 - This occurs when a sample that (1) exhibits no fluorescence *ex situ* and (2) is pathologically-confirmed as normal tissue, is classified as suspicious tissue during SOC surgery.
- Alteration to the Completeness of Cytoreduction (CC) Score – following the completion of the SOC surgery, the surgeon will document a CC score prior to fluorescence imaging using pgsitacianine. If the surgeon finds residual disease using fluorescence imaging that results in the increase of the CC score, this will be considered a CSE

The number and proportion (with corresponding two-sided exact 95% confidence intervals) of subjects with any CSE will be reported.

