3. STUDY PLAN

3.1 Overall Design

This Phase 2 study will be a an interventional, open-label, single arm trial where each patient is his/her own “intrapatient” control usin two Grou s. All patients will receive a single mg/kg dose of pegasitacianine prior to standard of care surgery.

Patients enrolled in Group 1 of the study will have a biopsy confirmed diagnosis of non-mucinous peritoneal carcinomatosis, defined as less than, or equal to 50% mucin in the sample, with a suspected Peritoneal Carcinomatosis Index (PCI) greater than or equal to . Group 2 of the study will include patients with a suspected PCI greater than or equal to and a biopsy confirmed diagnosis of mucinous peritoneal carcinomatosis, defined as > 50% mucin in the sample. A total of approximately 60 patients will be enrolled across both Groups. Enrollment will be open first to Group 1 with the opportunity to open Group 2 for enrollment following the demonstration of satisfactory pegasitacianine sensitivity and specificity values of 70% or greater in Group 1.

In both Groups 1 and 2, the surgeon will perform their SOC resection of visible metastases and image each resected specimen, and normal specimens on an area of normal tissue using the intraoperative NIR camera; no investigative NIR imaging of the peritoneal cavity will be performed at this time. The SOC specimens are to be resected upon the initiation of surgery and imaged on a section of normal tissue (i.e., mesentery). Specimen names and fluorescence status will be dictated by the surgeon and documented in the Imaging Workbook by the Clinical Research Coordinator.

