At the conclusion of SOC resection, the intraoperative NIR camera will be used to investigate the peritoneal cavity further for evidence of residual metastases highlighted by fluorescence using the approach that is performed for the calculation of the Peritoneal Carcinomatosis Index (i.e., 13 regions). Additional fluorescent specimens will also be imaged prior to excision and subsequently following resection on an area of normal tissue prior to sending all surgical specimens to pathology for examination. The fluorescence status of each specimen, as called out by the surgeon, will then be directly correlated to the histopathological outcomes of each specimen dictated in the final pathology report. This study design enables the calculation of pegsitacianine sensitivity, specificity, NPV, and PPV and the level of the specimens. Additionally, Completeness of Cytoreduction (CC) scores can be calculated following SOC resection and then adjusted following the additional resection of fluorescent metastases otherwise unknown to the surgeon. The schedule of events for this study is presented in Appendix 1.

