3.2 Imaging Assessments

Imaging assessments will include the calculation of mean fluorescence intensity (MFI) of all collected surgical specimens. Specimens will be imaged both prior to excision (for post-SOC specimens) and immediately following on a piece of representative normal tissue (all specimens). MFI values will be used to further compute SBR values for the collected specimens. Correlation of imaging observations to pathological outcomes of each specimen will be used to understand pegsitacianine performance (i.e., PPV, NPV, Sensitivity, Specificity). Imaging assessments may be performed at the Group level to accommodate for any confounding data between the two Groups.

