6.3 Surgery and Follow-up Visits (Group 1 and 2)

Procedures at the time of cytoreductive surgery

The following procedures will be performed on the day of surgery:

- Record the patient's vital signs (only if they were abnormal at dosing)

- Obtain blood for routine laboratory tests
- Record all medications being taken, including prescription, over-the-counter, and herbal medications
- Discuss with the patient any new or unexpected changes they are feeling
- Record any AEs

Once the patient is under anesthesia, some procedures will occur that would not normally be part of surgery if the patient were not in this study. The SOC surgical procedures will be allowed to continue with the addition of the steps listed below.

- During SOC resection, the surgeon will select up to 15 (10 suspected tumor and 5 normal) specimens that will be imaged using the intraoperative camera on a section of normal tissue following excision (*Note: NIR camera should not be used to examine the peritoneal cavity at this time*)
 - A total of up to 15 specimens are to be imaged: 5 representative normal pieces of tissue and 10 individual suspected tumor specimens
 - The SOC specimens are to be resected upon the initiation of surgery and imaged on a section of normal tissue (i.e., mesentery) immediately following the collection of all SOC samples
 - The width of the camera's field of view is to be confined to a distance of 10 cm. A surgical ruler is to be placed in frame to control the width of the field of view
 - Note: while there are no specimen size stipulations provided in this protocol, the samples must be able to be imaged within the 10 cm wide imaging window.
 - For samples with multiple nodules, individual nodules should be dissected away from the bulk sample and imaged individually as single specimens.
 - Representative normal sections of tissue should be imaged in an analogous manner
- Samples will be imaged using the NIR camera and fluorescence status and specimen name will be dictated by the surgeon for documentation by the clinical research coordinator in the provided Imaging Workbook
- Once the SOC resection is complete, the surgeon will dictate their completeness of cytoreduction score to the clinical research coordinator for documentation prior to examining the peritoneal cavity with the intraoperative NIR camera in search of additional fluorescent metastatic disease that was missed during SOC

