3. STUDY DESCRIPTION

3.1 Study Design

This Phase 2 study will be an interventional, open-label, single arm trial where each patient is his/her own “intrapatient” control using two Groups. All patients will receive a single █ mg/kg dose of pegsitacianine administered █ prior to standard of care surgery.

Patients enrolled in Group 1 of the study will have a biopsy confirmed diagnosis of non-mucinous peritoneal carcinomatosis, defined as less than 50% mucin in the sample, with a suspected Peritoneal Carcinomatosis Index (PCI) greater than or equal to 10. Group 2 of the study will include patients with a suspected PCI greater than or equal to 10 and a biopsy confirmed diagnosis of mucinous peritoneal carcinomatosis, defined as > 50% mucin in the sample. A total of approximately 60 patients will be enrolled across both Groups. Enrollment will be open first to Group 1 with the opportunity to open Group 2 for enrollment at the discretion of the sponsor.

In both Groups 1 and 2, the surgeon will perform their SOC resection of visible metastases and image each resected specimen, and normal specimens on an area of normal tissue outside of the surgical field using the intraoperative NIR camera; no NIR imaging of the peritoneal cavity will be performed at this time. At the conclusion of SOC resection, the intraoperative NIR camera will be used to investigate the peritoneal cavity further for evidence of residual metastases highlighted by fluorescence using an approach similar to that performed for the calculation of the Peritoneal Carcinomatosis Index (i.e., 13 regions). Additional fluorescent specimens will also be imaged on an area of normal tissue within the surgical field prior to sending all surgical specimens to pathology for examination. The fluorescence status of each specimen will then be directly correlated to the histopathological outcomes of each specimen. This study design enables the calculation of pgsitacianine sensitivity, specificity, NPV, and PPV. Additionally, Completeness of Cytoreduction (CC) scores can be calculated following SOC resection and then adjusted following the additional resection of fluorescent metastases. The schedule of events for this study is presented in [Appendix 1](#).

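### The written rule for the occult-disease CSE places the sample in the SOC phase, when the procedures allow no fluorescence search of the cavity

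*Protocol*

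**What the plan says.** Protocol 9.3 makes the subject-level CSE rate the primary objective. One CSE type is occult disease or a positive surgical margin. Its parent definition covers tumor found because of fluorescence that "otherwise went undetected during pre-operative imaging (PET, MRI) or by the surgeon during SOC surgery". The sub-bullet beneath it gives the operational rule. It begins "This occurs when a sample that (1) exhibits fluorescence" in situ, adds pathological confirmation as tumor, and ends with the requirement that the sample "is obtained by fluorescence during SOC surgery". SAP 5.1.1 carries the same rule.

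The procedures run in a different order:

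- Protocol 6.3, on the SOC resection step: "NIR camera should not be used to examine the peritoneal cavity at this time".
- Protocol 3.1, on the same step: "no investigative NIR imaging of the peritoneal cavity will be performed at this time". SAP 3.1 is broader: "no NIR imaging of the peritoneal cavity will be performed at this time".
- Protocol 3.2 limits imaging before excision to one kind of specimen: "Specimens will be imaged both prior to excision (for post-SOC specimens"; imaging after excision applies to all specimens.
- Protocol 3.1, on the search itself: "At the conclusion of SOC resection, the intraoperative NIR camera will be used to investigate the peritoneal cavity further".

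The synopsis endpoint and SAP Table 1 both describe residual disease detected once SOC resection is over.

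**The concern.** The rule requires two things that the procedures keep apart. In situ fluorescence and collection by fluorescence belong to the search after SOC resection. The timing condition belongs to the phase before it. A specimen that meets the first two therefore fails the third, and the reverse also holds.

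This sub-bullet is the only place where either document states when this CSE type occurs, and this type is the one closest to the primary objective. A programmer who follows the text exactly would leave out the intended events. One who follows the intent must override the written rule of the governing document. The trial is meant to inform power calculations for later studies (protocol 9.1), so the definition behind this rate should not depend on such a choice.

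**Working it through.** **Step 1. Conditions of the rule.** From protocol 9.3 and SAP 5.1.1: (A) fluorescent in situ; (B) tumor on pathology; (C) obtained by fluorescence; (D) obtained during SOC surgery.

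**Step 2. Specimens that a compliant procedure can produce** (protocol 3.1, 3.2, 6.3). B can be met by either kind.

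| Specimen | A: in situ status | C: found by fluorescence | D: during SOC |
|---|---|---|---|
| SOC specimen, suspected tumor or normal | No; imaged only after excision | No; chosen by the surgeon without NIR inspection | Yes |
| Additional fluorescent specimen | Yes; imaged before excision | Yes | No; search starts after SOC resection |

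No row meets A, C and D together.

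**Step 3. Could SOC surgery mean the whole operation?** The CC-score bullet in the same list of protocol 9.3 has the surgeon record a score once SOC surgery is complete and before any fluorescence imaging. In that list, SOC surgery is a phase that ends before the NIR search.

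**Step 4. Does the SAP repair it?** No. SAP 5.1.1 repeats the rule, SAP 1 gives the SAP precedence on analyses and reporting, and SAP 8 declares no deviations from the protocol.

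**Step 5. Size.** The documents give no assumed CSE rate or precision target, so there is no planned figure to reproduce. For 0 events in n subjects, the two-sided 95% Clopper-Pearson interval (the method in SAP 7.10.1.1) has lower limit 0 and upper limit 1 − 0.025^(1/n).

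- n = 60 (planned enrollment, all assumed evaluable): 1 − 0.025^(1/60) = 1 − 0.9404 = 0.0596, so 0 to 6.0%.
- n = 40 (the sample size planned at the outset): 1 − 0.025^(1/40) = 1 − 0.9119 = 0.0881, so 0 to 8.8%.

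This zero is produced by the definition and estimates nothing. For contrast, suppose the rule pointed to the post-SOC inspection. The rates below are assumptions, since the documents give none:

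| Assumed rate | Count | Exact 95% CI |
|---|---|---|
| 20% | 12/60 | 10.8 to 32.3% |
| 40% | 24/60 | 27.6 to 53.5% |
| 60% | 36/60 | 46.5 to 72.4% |

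Even at 20%, the lower limit of 10.8% lies above the 6.0% upper limit that the literal rule would report.

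**The case against.** The strongest reply is that nobody would apply the rule literally, and much of that stands. The synopsis, protocol 3.1 and SAP Table 1 all place the detection after SOC resection. The efficacy population requires the opportunity for post-SOC exploration. The specimen listing in SAP 7.10.2.1 separates SOC from fluorescence specimens and shows in situ and ex situ status, so the intended specimens can be identified. Each CSE type is summarised separately, so a component with no events would be noticed. A patient could also still be a responder through a tumor-negative SOC biopsy or a CC-score change.

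It can also be said that the terminology is loose. Protocol 6.3 introduces the intraoperative steps, including the NIR search, as additions to the continuing SOC procedures, and its NIR bar attaches to SOC resection. That shows inconsistent usage, but it does not rescue the rule, because the CC-score bullet beside it uses the narrow sense.

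A reader might also infer that the word *or* in the parent definition lets in deposits that the surgeon saw and knowingly left, provided imaging had missed them. The documents do not support that. After a negative, the ordinary sense is that neither source detected the tissue. The parent definition requires identification because of fluorescence, and the lead-in to 9.3 limits occult disease to disease that the surgeon did not know of. Protocol 3.1 and 6.3 likewise describe the search as being for disease unknown to the surgeon or missed. The clause is ambiguous and no more than that.

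**Conclusion.** The timing condition is wrong as written in both documents. It contradicts the imaging sequence, the stated endpoint and the neighbouring CC-score bullet. Its size is confined to one CSE component: under a literal reading, 0 compliant events (0/60, exact 95% CI 0 to 6.0%). This assumes that all 60 patients are evaluable and that sites follow the imaging sequence.

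Three stronger conclusions are not supported:

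- **That the trial will report no CSEs.** The intent is recoverable, and other CSE types remain available.
- **That the *or* clause inflates the rate by some number of points.** The documents give no count of deposits knowingly left and missed by imaging, so no figure can be derived.
- **That every lesion in a Peritoneal Carcinomatosis Index (PCI) region with known residual disease should be disqualified.** The cavity is divided into only 13 regions, so this would also discard genuinely occult deposits elsewhere in the same region. It would be a new endpoint rule and not a clarification.

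No sample-size or power figure depends on this point, because the study is not powered for hypothesis testing.

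**What to change.** In protocol 9.3 and SAP 5.1.1, in the sub-bullet for this CSE type, replace the closing words *during SOC surgery* with: *during the NIR inspection performed after completion of SOC resection and after the pre-NIR CC score is recorded*.

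In the same edit, clarify the parent clause. State that the tissue must not have been known to the surgeon before the NIR inspection, in line with the lead-in to 9.3. Also say explicitly whether pre-operative imaging must have been negative as well. The second item is the sponsor's choice; the present wording leaves it open.

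The cost is wording in two sections. The pre-NIR CC score is already dictated at that step under protocol 6.3, so the timing correction needs no new procedure or data item and applies to every patient, including those already treated. SAP 7.1 allows updates before database lock and requires a protocol amendment where a change in methods may affect the primary conclusions; this correction should follow that route.
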